5.3 Secondary Endpoints

- 5.3.1. Change from Baseline in pain at 1, 2 and 4 months (assessed by Visual Analogue Scale, VAS).
- 5.3.2. Change from Baseline in disability at 1, 2 and 6 months (assessed by Oswestry Disability Index, ODI).
- 5.3.3. Change from Baseline in health survey at 1, 2, 4 and 6 months (assessed by Short Form Health Survey, SF-12).
- 5.3.4. Change from Baseline in neuropathic pain at 1, 2 and 6 months (assessed by Douleur Neuropathique 4 Questions, DN4).
- 5.3.5. Assessment of improvement of pain with experimental procedure at 1, 2, 4 and 6 months (assessed by Patient Impression of Improvement, PGI-I).
- 5.3.6. Incidence of unanticipated adverse device effects.
- 5.3.7. Change in opioid intake in 6 months.
- 5.3.8. Adverse events related to procedures (experimental group and control group).
- 5.3.9. Assessment of subject satisfaction with experimental procedure at 2 and 6 months.

6. - ELIGIBILITY CRITERIA

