7.2 Randomization Process

The clinical investigation will be single-blind. The assignment to the type of surgical treatment is carried out randomly and open for the investigators but not for

the patients. Randomization will be done with concealment of the randomization sequence and it takes place after informed consent has been signed.

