7.4 Blinding

This study is single-blind.

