- 5-point scale where 1 is “very satisfied” to 5 that is “very dissatisfied”; their charging convenience and remote control use during the study visits: Months 2, 6 and if applicable at the Unscheduled visit. The responses will be summarized. Study personnel will be appropriately trained for administration of each test.

- Safety (device and procedures): Safety will be assessed by characterizing clinically meaningful change in adverse events at all study visits and in related to medical device or procedures.

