8.2 Adverse Device Effect (ADE)

An adverse event related to the use of a medical device.

This definition includes adverse events resulting from insufficient or inadequate instructions for use, deployment, implantation, installation, or operation, or any malfunction of the medical device.

This definition includes any event resulting from the use error or from intentional misuse of the medical device.

During this clinical investigation an event should be considered related to the device when it is the result of:

- The device components (e.g. lead, extension, Trial Simulator, Remote).
- The Therapy/simulation.

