8.7 Severity

The Investigator will use the following definitions to rate the severity of each adverse event:

- Mild: Awareness of a sign or symptom that does not interfere with the subject's usual activity or is transient, resolved without treatment and no sequelae.

- Moderate: Interferes with the subject's usual activity or requires symptomatic treatment.
- Severe: Symptom(s) causing severe discomfort with significant impact of the subject's usual activity and requires treatment.

8.8 Reporting.

According to current regulations, professionals must report those incidents that are associated with a medical device or with the information provided with the product and that incident is such that it has caused death or a serious deterioration in health, or if it occurs again it can cause them.

An incident is understood to be any malfunction, failure or deterioration of the characteristics or operation of a product, as well as any deficiency in the labelling or in the instructions for use that could or have led to death or serious deterioration of the condition health of a patient or a user. The types of adverse incidents that must be reported are the following:

1. Those that lead to death.
2. Those that give rise to a serious deterioration of the state of health of the patient, user or other person, such as:

- Illness or injury with threat to life.
- Permanent deterioration of a bodily function or permanent damage to a body structure.
- Process that requires medical or surgical intervention to avoid permanent deterioration of a bodily function or permanent damage to a body structure.

3. Potential incidents, which are those that could have led to death or a serious deterioration of health, but that have not occurred due to fortunate circumstances or the intervention of health personnel.

These incidents must be reported by the investigators. They must notify the sponsor of any serious incidents that may be related to the devices involved in the development of the investigation, through Annex III available at:

<https://www.aemps.gob.es/vigilancia/productosSanitarios/vig-prof-nota.htm#II>

And the sponsor must evaluate them and notify them to the surveillance points of medical devices of the CCAA, in accordance with the general guidelines established by the Medical Device Surveillance System for the notification of adverse incidents:

<https://www.aemps.gob.es/surveillance/healthproducts/professional-monitoring.htm>

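### The safety measure in 7.6 is undefined and the named safety endpoints count only attributed events, with no assessor named and sites aware of the arm; tabulate recorded events by arm regardless of relatedness

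*Combined protocol and SAP*

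**What the plan says.** Section 7.6 defines the safety assessment in one sentence: "Safety will be assessed by characterizing clinically meaningful change in adverse events at all study visits and in related to medical device or procedures".

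Section 5.3 names two safety endpoints. Item 5.3.6 is "Incidence of unanticipated adverse device effects". Item 5.3.8 is "Adverse events related to procedures (experimental group and control group". Both need a judgement on what caused the event.

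The rule for that judgement is in 8.2: "During this clinical investigation an event should be considered related to the device when it is the result of" device components or the therapy. No assessor is named there. Section 8.7 gives the site one rating task: "The Investigator will use the following definitions to rate the severity of each adverse event". In 8.8, investigators notify serious incidents that may be device-related and the sponsor evaluates them.

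On knowledge of the arm, 7.2 says "The assignment to the type of surgical treatment is carried out randomly and open for the investigators", and 7.4 adds only "This study is single-blind".

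On collection, 8.1 sends to the eCRF all serious adverse events and the adverse events of interest. Section 8.1.1 lists the latter: a procedure lasting more than one hour, surgical wound problems, and infection. Neither section makes recording depend on relatedness.

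**The concern.** Two weaknesses combine. First, the measure in 7.6 cannot be calculated as it stands. It gives no threshold, reference value, event window or denominator, and section 13 does not supply them: it offers general descriptive statistics and tests only the primary variable. Two analysts could report different safety results from the same records.

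Second, the endpoints that are countable depend on a causal label. Both arms share the caudal needle, the epidural electrode, contrast and sedation, so much of the true procedural risk is common. In the control arm, however, 9.1 has the generator at zero voltage. Someone who knows this can hardly call a control event the result of the therapy, whereas the same event after radiofrequency can be called exactly that. Labels may then diverge where risks do not.

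The statement of purpose in the Summary suggests that epidural PRF can be safe. A safety statement from this trial should rest on counts that need no causal judgement by someone who may know the arm.

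**Working it through.** **1. The plan's own figure.** No figure is given for any safety endpoint. The only denominator is 62 per group, from 7.3, set for the VAS endpoint. It reproduces: a two-sided t-test with difference 20 mm, SD 30 mm, alpha 5% and power 90% needs 48.26, so 49 evaluable per arm; 49 / 0.80 = 61.25, so 62. It is used below only as the number treated per arm.

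**2. What the text settles.**

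| Question | Answer in the plan |
|---|---|
| What is a meaningful change in events? | Not defined (7.6, 13) |
| Who judges it? | Not stated (7.6) |
| When is an event device-related? | When it results from components or therapy (8.2) |
| When is an event procedure-related (5.3.8)? | No rule |
| Who judges relatedness? | Not stated (8.2); the sponsor evaluates notified incidents (8.8) |
| Who rates severity? | The investigator (8.7) |
| Do site investigators know the arm? | Yes (7.2) |
| Is there blinded adjudication? | None described (3.8, 7.4, 8) |
| What is recorded regardless of relatedness? | Serious events and listed events of interest (8.1, 8.1.1) |

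The example components in 8.2 (a lead, an extension, a trial simulator, a remote) are also not those in the device list in 3.3, so the device rule gives little guidance here.

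**3. Effect of unequal labelling.** Let p be the true event risk, equal in both arms, and let a_E and a_C be the proportions of events called related in the experimental and control arms. The observed rates of related events are p × a_E and p × a_C. The apparent risk ratio is a_E / a_C, which does not depend on p. The apparent risk difference is p × (a_E − a_C). The documents give none of these values, so all are assumptions.

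| p | a_E / a_C | Observed rates | Risk difference | Risk ratio |
|---|---|---|---|---|
| 10% | 90% / 70% | 9% v 7% | 2 points | 1.29 |
| 20% | 90% / 70% | 18% v 14% | 4 points | 1.29 |
| 30% | 90% / 70% | 27% v 21% | 6 points | 1.29 |
| 10% | 90% / 50% | 9% v 5% | 4 points | 1.8 |
| 20% | 90% / 50% | 18% v 10% | 8 points | 1.8 |
| 30% | 90% / 50% | 27% v 15% | 12 points | 1.8 |

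With the labelling reversed, the ratios are 0.7 / 0.9 = 0.78 and 0.5 / 0.9 = 0.56. The direction cannot be known in advance.

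**4. If someone tested it.** With 62 per arm and the normal approximation, the chance of a two-sided 5% result in the favoured direction rises from 2.5% to 6–12% (90/70) or 14–37% (90/50). An exact test would give lower figures. No such test is planned, so this only shows the scale.

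**5. The alternative count.** If events are counted regardless of relatedness, the expected rates are p and p, and a_E and a_C drop out. This mechanism then has no effect.

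**The case against.** The strongest reply is that the plan's safety work does not hang on attribution. All serious events and the listed events of interest are recorded with no relatedness condition, 8.1.1 defines an adverse event as covering related and unrelated occurrences, and 3.8 sets up an independent DSMB. This stands as far as collection and oversight go. It does not say what will be reported: 5.3 lists no all-causality count, and the DSMB is not described as adjudicating events blind to arm.

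A reader might infer that the operator or the site investigator decides relatedness. The documents do not say so. They give the investigator the severity rating and incident notification, and they give the sponsor the evaluation of notified incidents. What they support is an unnamed assessor in a trial whose sites know the arm.

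A reader might also argue that change in adverse events is meaningless because events have no baseline. That goes too far: 7.5.2 and Table 1 include adverse event assessment at Baseline. The fault is the missing definition.

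Finally, it can be said that this is a secondary, descriptive outcome, and that an all-event count has problems of its own. Both are right. Section 13 plans no between-arm safety test. Section 8.1 does not collect every non-serious event and leaves non-serious leg and back pain to investigators' discretion. Procedure time over one hour may differ by arm by design, because 9.2 adds level-by-level placement and stimulation. These facts limit what the replacement count should contain; they do not rescue the sentence in 7.6.

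**Conclusion.** The point holds for the reported safety measure. The criterion in 7.6 is undefined, and 5.3.6 and 5.3.8 count attributed events only, with no named assessor, no procedure-relatedness rule, no described blinded adjudication and sites aware of allocation. The descriptive arm contrast is therefore open to bias of unknown direction.

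Its size cannot be derived from the documents. Under the assumed labelling splits the apparent risk ratio is 1.29 to 1.8, or 0.78 to 0.56, when true risks are equal. That rests on equal true risk and on labelling that differs by arm; the plan permits the latter but nothing shows it will happen.

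The documents do not support reading this as a failure of the whole safety assessment, or as a threat to the primary analysis or the sample size. It should be corrected because a concrete measure is available from data already planned.

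**What to change.** Replace the sentence in 7.6 with wording such as:

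*Number and percentage of treated patients with at least one serious adverse event, and with at least one recorded adverse event of interest (wound problem, infection), from the start of the procedure to 6 months, by randomised arm, regardless of relatedness, with the risk difference and 95% CI.*

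Then:

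- Tabulate procedures longer than one hour separately, because the radiofrequency arm adds steps by design.
- Keep the attributed events of 5.3.6 and 5.3.8 as a second table.
- List events between baseline and the procedure separately for the ITT-B population of 7.10. The treated denominator above matches that section's ITT definition.
- Do not present the count as a total of all non-serious events, since 8.1 does not collect them.

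The cost is a rewording of 7.6, a cross-reference from 5.3.6 and 5.3.8, one table and a short listing. No new data are needed. The downside is small: the counts include unrelated events and so look higher. One further sentence stating who judges relatedness, and by what rule for the procedure, would make the second table easier to interpret.

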7.7 Early Subject Withdrawal

Subjects may be withdrawn early from the study for a number of reasons, including but not limited to:

- Subject request.
- Investigator request.
- Subject lost to follow up.
- Subject death.
- Intolerable adverse events.

If a subject is discontinued from the study early, a Termination CRF will be completed describing the reason for discontinuation. The Investigator should make all attempts to conduct a visit within 10 days (± 4 days) after withdrawal from the study. If a subject has withdrawn consent for the study, or is lost to follow-up, the completion of this visit is not imperative. In situations where study withdrawal is due to an adverse event, subjects will be followed until resolution of that adverse event or determination that the subject's condition is stable.

In case of an Early Subject Withdrawal the subject will be assessed for adverse events, if any, and medication use. This will be documented on an Unscheduled Visit CRF.

In case the Early Subject Withdrawal happened at a study specific follow-up visit (see Table 1. Schedule of Events) no Unscheduled Visit CRF need to be completed.

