7.3 Sample Size and justification

Pain reduction at least thirty millimeters between the baseline visit and the 6 months visit in patients assigned to the experimental group evaluated by the Visual Analogue Scale (VAS). Pain reduction of twenty millimeters less in the experimental group than in the control group since the baseline visit and the 6 months visit evaluated by the Visual Analogue Scale (VAS).

To achieve a power of 90.00% to detect differences in the contrast of the null hypothesis $H_0: \mu_1 = \mu_2$ through a bilateral T-Student Test for two independent samples, taking into account that the level of significance is 5%, and assuming that the mean of the difference in VAS of the 6-month radiofrequency plus steroid group is 40 mm, the average of the control group is 60 mm and the standard deviation of both groups is 30 mm, with an estimate of losses of the 20%, it will be necessary to include 62 patients per group, total of 124 patients.

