7.5.8. Unscheduled Visit

At this clinic visit the subject will undergo the following evaluations:

- Any change of medication will be collected.
- Subjects will be asked to fill out standard questionnaires to assess (VAS, ODI, SF-12, DN4 and PGI-I).
- Subjects will be assessed for possible adverse events, if any.
- Study completion (if applicable).
- Adverse event monitoring.
- Deviation monitoring.
- Subject questionnaire of treatment satisfaction.

All applicable information will be documented on a CRF.

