7.6 Evaluation Endpoints

▪ Primary endpoint

Visual Analogue Scale (VAS): The VAS measures the pain intensity reported by the subject. Subject scores the intensity of pain on a 10 mm line. The VAS in this study consists of a 10 mm line with one indicating “No Pain” and the other end indicating “Worst imaginable pain”. Upon completion by the subject VAS scores will be measured and converted to a numeric value (0.0 mm to 10.0 mm) by site staff personnel. VAS is the most widely used outcome measure in assessing pain due to its documented reliability and validity, ease in administration, and minimal training requirements for the administrator.

Subjects will complete a mean VAS score for leg and back pain: at Baseline, months 1, 2, 4, 6 and if applicable at the Unscheduled visit. The change in leg and back pain VAS scores, the percentage change in leg and back pain VAS scores, and the responder rate for leg and back pain will be calculated and summarized for each visit.

▪ Secondary Endpoints.

- Oswestry Disability Index (ODI): The ODI measures functional disability as reported by the subject. Subjects will complete ODI during the study visits: at Baseline, months 1, 2, 6 and if applicable at the Unscheduled visit. The changes in functional disability will be summarized as continuous variables.

- Short Form Health Survey (SF-12): The SF-12 measure health status reported by subject at: Baseline, months 1, 2, 4, 6 and if applicable at the Unscheduled visit. The changes in health status will be summarized as continuous variables.

- Douleur Neuropathique 4 Questions (DN4): The DN4 measures the neuropathic pain reported by the subject. Subjects will complete DN4 during the study visits: at Baseline, months 1, 2, 6 and if applicable at the Unscheduled visit. The changes in neuropathic pain will be summarized as continuous variables.

- Patient Impression of Improvement questionnaire (PGI-I): The PGI-I measure subjective improvement in pain. Subjects will complete PGI-I form during the study visits at: month 1, 2, 4, 6 and if applicable at the Unscheduled visit.

- Medication Usage: morphine equivalent units of opioid medications; other non-opioid pain medications. Assessed at: Baseline, months 1, 2, 4, 6 and if applicable at the Unscheduled visit.

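### Section 7.7 conflicts with 7.5.8 and Table 1 on the VAS at early withdrawal, and provides no month-6 VAS for treated patients withdrawn at investigator request or for an adverse event who still consent

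*Combined protocol and SAP*

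**What the plan says.** All references are to the combined protocol and SAP.

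- **Exit visit, content (7.7).** "In case of an Early Subject Withdrawal the subject will be assessed for adverse events, if any, and medication use". The next sentence gives the form: "This will be documented on an Unscheduled Visit CRF".
- **Exit visit, obligation (7.7).** It is best effort: "The Investigator should make all attempts to conduct a visit within 10 days (± 4 days) after withdrawal from the study". There is an exemption: "If a subject has withdrawn consent for the study, or is lost to follow-up, the completion of this visit is not imperative". A patient who withdraws at a scheduled follow-up visit needs no Unscheduled Visit CRF.
- **Unscheduled Visit, content (7.5.8).** "Subjects will be asked to fill out standard questionnaires to assess (VAS, ODI, SF-12, DN4 and PGI-I" and so on, with satisfaction, medication and adverse events. The Unscheduled column of Table 1 agrees.
- **VAS timing (7.6).** The list of time points ends with the Unscheduled Visit: "Subjects will complete a mean VAS score for leg and back pain: at Baseline, months 1, 2, 4, 6 and if applicable at the Unscheduled".
- **Reasons for leaving (7.7).** The list is open-ended and includes the investigator's request and adverse events that cannot be tolerated. After withdrawal for an adverse event, follow-up continues until the event has resolved or the patient is stable. Nothing is said about pain or the other outcomes.
- **Knowledge of the arm (7.2).** "The assignment to the type of surgical treatment is carried out randomly and open for the investigators".
- **Losses (7.3).** The sample size is set "with an estimate of losses of the 20" per cent.
- **Primary endpoint and analysis (5.2, 13).** The VAS change from baseline to 6 months is compared by t-test or Mann-Whitney test. No method for a missing month-6 value is given.

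**The concern.** There are two separate problems.

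The first is a conflict of text. Section 7.7 is the specific rule for early withdrawal, so a site may follow it and see the patient without taking a VAS. A site that follows 7.5.8 and Table 1 takes one. The adverse event assessment does not fill the gap, because 8.1 exempts leg and back pain from adverse event reporting unless it is serious.

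The second matters more for the primary comparison. Treatment is given once, so after that session leaving the study stops no study treatment; it stops measurement. A patient withdrawn for an adverse event may still be seen by the site and may still consent, yet the plan asks for no further pain score. The request to withdraw can come from an investigator who knows the arm. If those who leave differ in pain from those who stay, and differ more in one arm than in the other, the month-6 comparison is biased. Section 13 offers nothing to limit that.

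**Working it through.** **1. The sections side by side**

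| Situation | VAS at exit? | VAS at month 6? |
|---|---|---|
| Withdrawal at a scheduled follow-up visit (7.7, 7.5.4 to 7.5.7) | Yes, part of that visit | Only if that visit is month 6 |
| Withdrawal between visits, reading 7.7 | Not named | No |
| Withdrawal between visits, reading 7.5.8 and Table 1 | Yes | No |
| Consent withdrawn or lost to follow-up (7.7) | Exit visit not imperative | No |

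The conflict affects only rows 2 and 3. The last column shows that settling it would not supply the primary endpoint: an exit VAS about 10 days after withdrawal is not a month-6 VAS.

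**2. What the analysis does with the gap**

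Section 7.10 defines ITT as all treated subjects and PP as treated subjects with the primary assessment. A t-test on the change score needs both values. With no rule for a missing month-6 VAS, the primary ITT comparison can use only patients who have it, which is in effect the PP set.

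**3. The plan's own sample size**

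Inputs from 7.3: difference 60 − 40 = 20 mm, SD 30 mm, two-sided 5%, power 90%, losses 20%.

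- Noncentral t: 49 per group gives power 0.904.
- Inflation: 49 / (1 − 0.20) = 61.25, rounded up to 62. This matches the stated 62 per group.
- The normal approximation gives 48, and 48 / 0.80 = 60, close to the stated figure.

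Planned losses: 0.20 × 62 = 12.4 per arm, or 0.20 × 124 = 24.8 in total.

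Power at the same 20 mm effect is 0.904 with 49 per group analysed, 0.934 with 55 (about half the losses recovered) and 0.958 with 62. Power is already at its target without recovery, so the issue is bias.

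**4. Size of a possible bias**

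The documents do not split the losses by reason, so the following are assumptions:

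- A fraction f of one arm's losses is recoverable, meaning the patients still consent and can be contacted.
- Those patients are D mm worse than that arm's completers.
- All other losses, in both arms, resemble completers.

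Shift of the completer contrast relative to all treated patients = 0.20 × f × D.

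| f | Patients in the arm (12.4 × f) | D = 10 mm | D = 20 mm | D = 30 mm |
|---|---|---|---|---|
| 0.25 | 3.1 | 0.5 | 1.0 | 1.5 |
| 0.50 | 6.2 | 1.0 | 2.0 | 3.0 |
| 1.00 (upper bound) | 12.4 | 2.0 | 4.0 | 6.0 |

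Against 20 mm, 0.5 to 3 mm is 2.5% to 15%, and the upper-bound row is 10% to 30%.

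Check of the largest cell: if completers differ by 20 mm and the lost patients by 20 − 30 = −10 mm, the difference in all patients is 0.8 × 20 + 0.2 × (−10) = 14 mm, a shift of 6 mm.

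The sign depends on the arm. Worse outcomes among those lost from the experimental arm make completers overstate the benefit; among those lost from the control arm, they make completers understate it.

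**The case against.** The case on the other side is substantial.

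- **The exit VAS is provided for elsewhere.** A reader might infer from 7.7 that no pain score is planned at withdrawal. The documents do not support that. Section 7.7 does not say that its two items are the only ones, and it uses the CRF of a visit that includes VAS. Patients who withdraw at a scheduled follow-up visit give a VAS in any case. What stands is a conflict, which 7.6 does not settle because it asks for VAS at an Unscheduled Visit only where applicable.
- **Not all losses are recoverable.** A reader might charge the full 20%, and so the 2 to 6 mm, to this rule. The 20% covers losses from any cause, including death, loss to follow-up and withdrawn consent, which no wording of 7.7 could recover. Similar outcome-related loss in both arms would also largely cancel.
- **Selective removal is not shown.** A reader might infer that investigators will take patients out according to arm. The documents show only that this is possible: the reasons are permissive, each exit needs a Termination CRF stating the reason, and 7.8 expects all subjects to complete the visits to month 6. That expectation does not override 7.7, however, and gives no route to stay in outcome follow-up once withdrawn.
- **Better collection does not replace an analysis rule.** This is correct. Some month-6 values will be missing under any wording, and section 13 would still need to say how they are handled.

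**Conclusion.** The point holds in two parts. First, 7.7 conflicts with 7.5.8 and Table 1 on whether VAS is taken at a withdrawal visit, and the sections must be reconciled. Second, 7.7 provides no outcome follow-up for treated patients withdrawn at investigator request or for an adverse event, so their month-6 VAS is lost even when they still consent, and section 13 has no method for it. The second part carries the weight, because an exit VAS cannot stand in for the primary endpoint.

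The size is illustrative: about 0.5 to 3 mm of the planned 20 mm if a quarter to a half of one arm's losses are recoverable and 10 to 30 mm worse than completers, with 2 to 6 mm as the upper bound if all that arm's losses were of this kind. The fractions and the pain differences are assumptions; only the 20% loss, the 62 per arm and the 20 mm come from the plan. The sample size is reproduced and stays at 62 per arm, and there is no power shortfall. The change should be made because it reduces avoidable bias at little cost.

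**What to change.** 1. **Withdrawal visit.** State in 7.7 that this visit includes the 7.5.8 assessments, VAS included, together with adverse events and medication use. This brings 7.7 into line with 7.5.8 and Table 1.
2. **Outcome follow-up.** In 7.7, separate withdrawal of consent from other reasons for stopping. State that treated subjects who still consent and can be contacted are asked to complete the remaining scheduled outcome assessments, at least the month-6 VAS. Edit the list of reasons in 7.7 to agree. Framed as a request, this governs data collection only: it leaves clinical decisions and the right to withdraw untouched, and avoids the contradiction that a flat bar on withdrawal would create with the listed reasons.
3. **Companion change.** Section 13 should say how a month-6 VAS that is still missing is handled, since items 1 and 2 will not recover every value.

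Cost: a short edit to 7.7, some follow-up visits that would otherwise be dropped, and a few minutes of questionnaires per exit visit. The visits and forms are already planned, and the sample size does not change.
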